Any disease in the decompensation stage;
Neuralgic and psychological disorders that interfere with the study;
Cancer;
Non-transportable patients;
Patients who do not reside in Almaty;
Patients who have refused to participate in the study.

Examined for eligibility - 76 people;

Confirmed eligible - 60 people. According to our strict exclusion criteria, we had to remove 16 people [8 – oncological patients, 5 – moved house, 3 patients refused to participate];

Included in the study - 60 patients;

Completing follow-up and analysed - 60 patients.

Statistical Analysis Plan

Gut microbiota:

IBM SPSS ver. 23.0 (Chicago, IL, USA) was used to determine the statistical significance of the obtained data. All the indicators were verified for compliance with the law on normal distribution. If the variables obeyed this law, the Student's paired t-test was applied to determine statistical significance between the values before and after milk intake. Otherwise, the Wilcoxon sign rank criterion was used.

A single-factor analysis of variance was employed to verify the effect of administering freeze-dried mare's milk, which could potentially affect the indicators of gut microbiota.

Antiphospholipid antibodies:

The 95% confidence interval for aPL value was calculated for both median and mean. The confidence interval for the latter one was calculated in the descriptive statistics menu in IBM SPSS ver. 23.0 (Chicago, IL, USA).

It is necessary to find the value of the confidence coefficient (Student's criterion (t)) in the table of critical t-values, considering the total number of respondents (n) to find out a confidence interval for the median with a given confidence probability (p). After that, the calculation of the natural integer number (C) is needed for such a probability value: $C_p = (n/2 - t(p) \sqrt{n}/2)$. The lower confidence limit for the median is $X (C_p)$, where X is the ordinal number of the value in the ranked variation series corresponding to the lower boundary of the confidence interval. The upper confidence limit for the median is $X (n + 1 - C_p)$, where X is the ordinal number of the value in

the ranked variation series corresponding to the upper boundary of the confidence interval.

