If the normal distribution law is followed, the Student's paired t-test was used to determine statistical significance between values before and after freeze-dried mare's milk. If not, the Wilcoxon sign rank criterion was used for intergroup comparison. One-way analysis of variance (ANOVA) was used to determine the relationship between the mare's milk prescription factor and aPL levels in both groups.

Quality of life:

IBM SPSS ver. 23.0 (Chicago, IL, USA) was used to determine the statistical significance of the obtained data. All the indicators were verified for compliance with the law on normal distribution. If the variables obeyed this law, the Student's paired t-test was applied to determine statistical significance between the values before and after milk intake. Otherwise, the Wilcoxon sign rank criterion was used.

A single-factor analysis of variance was employed to verify the effect of administering freeze-dried mare's milk, which could potentially affect the quality-of-life scores.

Results section

Gut microbiota analysis.

In the main group, after taking freeze-dried mare's milk, there was a decrease in the content of bacteria phyla Bacteroidetes, Proteobacteria, Verrucomicrobia and Chloroflexi (by 3.03%, 2.83%, 0.47% and 0.16, respectively), and an increase in the content of bacteria phyla Nitrospirae, Tenericutes, Cyanobacteria, Spirochaetes, Euryarchaeota, Actinobacteria and Firmicutes (by 0.02 %, 0.05%, 0.15%, 0.17%, 0.24%, 1.42% and 7.62%, respectively).

The Fusobacteria phylum was absent according to the results of mare's milk intake in all respondents. The Elusimicrobia phylum, on the contrary, was present in some respondents as a result of therapy.

Attention is also drawn to the presence of the Synergistetes phylum, which was absent in the control group both before and after therapy. Moreover, the difference between the Firmicutes, Proteobacteria, Chloroflexi, Cyanobacteria and Synergistetes phyla was statistically significant (Table 1).

Table 1. The percentage terms of all phyla of the gut microbiota in the main group before and after taking freeze-dried mare's milk (CI - confidence interval).

Phylum name	Before	After	95% CI (t-student)	p (t-student)
Bacteroidetes	32,32%	29,43%	-0,01; 0,07	0,178
Firmicutes	45,31%	51,87%	-0,09; -0,02	0,001
Proteobacteria	9,25%	6,52%	0,1; 0,28	<0,001
Actinobacteria	3,75%	4,9%	-0,15; 0,14	0,951
Euryarchaeota	1,28%	1,52%	-0,42; 0,1	0,204
Verrucomicrobia	1,29%	0,83%	-0,09; 0,32	0,223

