Chloroflexi	0,23%	0,07%	0,04; 0,28	0,011
Cyanobacteria	0,16%	0,31%	-1,95; -0,17	0,028
Spirochaetes	0,08%	0,25%	-0,51; 0,17	0,324
Nitrospirae	0,01%	0,03%	-0,07; 0,02	0,235
Tenericutes	0,04%	0,09%	-0,2; 0,01	0,491
Fusobacteria	0,07%	0,00%	-0,05; 0,2	0,247
Elusimicrobia	0,00%	0,11%	-0,24; 0,02	0,109

Synergistetes	0,01%	0,09%	-0,14; -0,02	0,009
---------------	-------	-------	--------------	-------

In the control group, after taking freeze-dried mare's milk, there was a decrease in the content of bacteria phyla Bacteroidetes, Firmicutes, Chloroflexi and Cyanobacteria (by 2.5%, 0.4%, 0.07% and 0.07%, respectively), and an increase in the content of bacteria phyla Spirochaetes, Tenericutes, Fusobacteria, Verrucomicrobia, Proteobacteria, Euryarchaeota and Actinobacteria (by 0.005%, 0.01%, 0.04%, 0.24%, 0.26%, 0.48% and 3.56%, respectively).

The Nitrospirae and Elusimicrobia phyla were absent as a result of taking mare's milk in all respondents of the control group. At the beginning of therapy, some respondents were found to have bacteria of the Caldithrix phylum, which were absent during the repeated measurement. The Thermotogae phylum was found in several members of the control group during two measurements.

Moreover, the difference between the Actinobacteria and Chloroflexi phyla in the control group was statistically significant (Table 2).

Table 2. The percentage terms of all phyla of the gut microbiota in the control group after 2 stool tests (CI - confidence interval).

Phylum name	First test	Second test	95% CI (t-student)	p (t-student)
Bacteroidetes	32,27%	29,77%	-0,06; 0,08	0,754
Firmicutes	46,5%	46,1%	-0,06; 0,07	0,899
Proteobacteria	7,65%	7,91%	-0,1; 0,12	0,823
Actinobacteria	5,8%	9,36%	-0,46; -0,1	0,003
Euryarchaeota	0,39%	0,87%	-0,74; 0,24	0,209
Verrucomicrobia	1,72%	1,96%	-0,97; 0,85	0,871
Chloroflexi	0,10%	0,03%	0,002; 0,15	0,044
Cyanobacteria	0,41%	0,34%	-1,42; 1,89	0,728
Spirochaetes	0,007%	0,012%	-0,01; 0,004	0,324
Nitrospirae	0,01%	0,00%	-0,01; 0,02	0,324
Tenericutes	0,04%	0,05%	-0,12; 0,1	0,857
Fusobacteria	0,01%	0,05%	-0,13; 0,05	0,357
Elusimicrobia	0,03%	0,00%	-0,01; 0,07	0,090
Caldithrix	0,02%	0,00%	-0,01; 0,03	0,160
Thermotogae	0,02%	0,01%	-0,03; 0,06	0,454

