The proportion of Bacteroidetes and Firmicutes in the gut microbiota is most significant. Summarizing their values in the main and control groups, we can see that their content increased in the former and decreased in the latter. Statistical analysis revealed a significant difference in the content of these phyla between the main group compared to the control group (Table 3).

Table 3. The percentage terms of Bacteroidetes and Firmicutes phylum in the main and control groups.

Main group			Control group		
Bacteroidete s+Firmicutes (before)	Bacteroidetes +Firmicutes (after)	p (Wilcoxon)	Bacteroidete s+Firmicutes (first test)	Bacteroidetes +Firmicutes (second test)	p (Wilcoxon)
77,63%	81,3%	0,026	78,76%	75,87%	0,213

To determine the effect of freeze-dried mare's milk on the gut microbiota at the phylum level, a one-factor analysis of variance was performed. A statistically significant relationship between such a factor as the administration of freeze-dried mare's milk was revealed in the Firmicutes, Elusimicrobia and Proteobacteria phyla (Table 4).

Table 4. The relationship between the use of prescribed freeze-dried mare's milk and indicators of gut microbiota at the phylum level.

Phylum name	p (One-way ANOVA)
Bacteroidetes	0,180
Firmicutes	0,048
Proteobacteria	0,043
Actinobacteria	0,186
Euryaychaeota	0,403
Verrucomicrobia	0,583
Chloroflexi	0,220
Cyanobacteria	0,280
Spirochaetes	0,340
Nitrospirae	0,143
Tenericutes	0,657
Fusobacteria	0,140
Elusimicrobia	0,044
Bacteroidetes + Firmicutes	0,037

Overall, the intake of freeze-dried mare's milk by post-COVID patients primarily contributed to an increase in the content of the sum of two major phyla of gut microbiota — Bacteroides and Firmicutes, with the latter being particularly significant. There is also a notable decrease in the number of bacteria from the Proteobacteria phylum in the main group, which includes representatives of pathogenic microflora.

Antiphospholipid antibody analysis.

29 out of 30 main group patients (96.67%) had normal IgM and IgG levels before taking freeze-dried mare's milk. In the case of the control group, aPL levels were normal in all respondents. The aPL levels were normal in patients of both groups after the second ELISA (Table 5).

Table 5. Antiphospholipid antibody scores of each patient in the main and control groups after two assays (aPL -antiphospholipid antibodies).

Main group		Control group					
aPL (before)		aPL (after)		aPL (first assay)		aPL (second assay)	

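### None of Table 4's four nominal between-group microbiome results survives multiplicity correction, so the stated effect of the milk is exploratory, and Table 3 does not contain the between-group test credited to it

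*Combined protocol and SAP*

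**What the plan says.** The gut microbiota part of the Statistical Analysis Plan (SAP) specifies paired t or Wilcoxon tests before and after, plus a single-factor ANOVA for the effect of the milk, "which could potentially affect the indicators of gut microbiota". It does not say whether the ANOVA variable is the second-test value or the change, or on which scale. No significance level, primary outcome, family of tests or multiplicity rule is visible.

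The Results section, Gut microbiota analysis, then says:

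- Above Table 3, on Bacteroidetes plus Firmicutes: "Statistical analysis revealed a significant difference in the content of these phyla between the main group compared to the control group".
- Above Table 4, that a statistically significant relationship with the milk "was revealed in the Firmicutes, Elusimicrobia and Proteobacteria phyla".
- Below Table 4, that milk intake "primarily contributed to an increase in the content of the sum of two major phyla of gut microbiota", and: "There is also a notable decrease in the number of bacteria from the Proteobacteria phylum in the main group".

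The Brief Summary cites earlier findings of greater microbiome diversity and more short-chain-fatty-acid-secreting bacteria, and gives their confirmation as the aim. Stage II of the Detailed Description asks more broadly about the impact of the milk on the gut microbiome.

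**The concern.** Table 4 is the only place where the two arms are compared on the microbiome. It has 14 rows, and the four results below 0.05 all lie close to that limit. When many tests are run without a rule fixed beforehand, a few such values cannot carry a conclusion of effect.

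The text above Table 3 adds to this by describing two within-arm tests as a between-group finding. A change that is significant in one arm and not in the other is not a test of the difference between them. The untreated arm shows why within-arm p-values are weak evidence of effect: there too, "the difference between the Actinobacteria and Chloroflexi phyla in the control group was statistically significant" (Table 2, p=0.003 and 0.044), while Table 4 gives between-group p-values of 0.186 and 0.220 for these phyla.

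At stake is whether the trial reports an effect of the milk or a set of exploratory signals. The protocol goes on to plan recommendations for managing patients after COVID-19, so the wording matters.

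**Working it through.** **Inputs.** Table 4 lists 13 phyla and the sum. The four smallest p-values are 0.037 (sum), 0.043 (Proteobacteria), 0.044 (Elusimicrobia) and 0.048 (Firmicutes). The other ten run from 0.140 to 0.657. A two-sided 0.05 level is assumed, from the results that the text calls significant.

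**The plan's own count.** Unadjusted, 4 of 14 rows fall below 0.05: the three named phyla and the sum. This matches the text and table.

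**Correction over 14 rows.** BH: q at rank i is the smallest value of p × 14/rank at rank i or later. Holm: p × (14 − rank + 1), never allowed to decrease.

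| Rank | Row | p | p × 14/rank | BH q | Holm product | Holm p |
|---|---|---|---|---|---|---|
| 1 | Sum | 0.037 | 0.518 | 0.168 | 0.037 × 14 = 0.518 | 0.518 |
| 2 | Proteobacteria | 0.043 | 0.301 | 0.168 | 0.043 × 13 = 0.559 | 0.559 |
| 3 | Elusimicrobia | 0.044 | 0.205 | 0.168 | 0.044 × 12 = 0.528 | 0.559 |
| 4 | Firmicutes | 0.048 | 0.168 | 0.168 | 0.048 × 11 = 0.528 | 0.559 |

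At rank 5, 0.140 × 14/5 = 0.392, so later rows do not lower the q-values.

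**Correction over the 13 phyla, without the sum.** BH: 0.048 × 13/3 = 0.208 for all three. Holm: 0.043 × 13 = 0.559, carried to the other two.

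**Rounding.** With each p lowered by 0.0005, BH is 0.0475 × 14/4 = 0.166 and 0.0475 × 13/3 = 0.206.

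**Omitted phyla.** Synergistetes is in Table 1, and Caldithrix and Thermotogae are in Table 2. None of them is in Table 4. With 16 phyla, even if all three had p=0, the named phyla would have q = 0.048 × 16/6 = 0.128. Including the three could change their own results but cannot rescue the named ones.

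**Within-arm changes.** Table 1 has 14 rows. Bonferroni gives 0.001 × 14 = 0.014 for Firmicutes and less than 0.014 for Proteobacteria, so both stand as before-after changes. Elusimicrobia does not: "The Elusimicrobia phylum, on the contrary, was present in some respondents as a result of therapy", yet its paired p is 0.109.

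**Table 3 against its sentence.** The table holds one Wilcoxon p-value per arm: 0.026 for the main group (77.63% to 81.3%) and 0.213 for the control group (78.76% to 75.87%). The between-group test of the sum is the last row of Table 4 (p=0.037, unadjusted).

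**Aim against analysis.** Tables 1 to 4 contain phylum percentages only. No diversity index and no analysis of short-chain-fatty-acid producers is visible. The part of the results not available for this review lies between Tables 5 and 8, within the antibody section, and is unlikely to contain one.

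**The case against.** The strongest reply has five parts.

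1. *Four of 14 is more than chance predicts.* At 0.05, 14 × 0.05 = 0.7 false positives are expected, and four or more would have probability 0.004 under independence. But the rows are not independent: the sum contains Firmicutes, and percentages of one whole are correlated. The count argues against inferring that the milk has no effect, a reading that failure to survive correction does not support. It does not establish any one result.

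2. *The Proteobacteria statement is worded as a change in the main group, and Table 1 supports it.* This stands. A reader might infer that the decrease itself is unsupported, but it is well supported as a before-after change. Control Firmicutes, Proteobacteria and the sum also did not change significantly (0.899, 0.823, 0.213). What lacks support is the attribution to the milk.

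3. *Singling out the sum as unplanned is uneven.* This stands. The SAP names no individual phylum either, so all 14 rows are equally unspecified. The sum would pass at 0.037 only as a single pre-specified test, and nothing visible pre-specifies it.

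4. *The microbiome question is answered.* In part. The Stage II question is addressed at phylum level, so it would be wrong to infer that the study leaves its microbiome question wholly open. Only the Brief Summary's diversity and short-chain-fatty-acid aim lacks a visible analysis.

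5. *BH at 5% is a choice.* It is, but Holm agrees, and so does every family tried here.

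A reader might also rebuild between-group changes from the intervals in Tables 1 and 2 to test Table 4. The documents do not support this, because the interval scales are unstated and appear mixed. In Table 1 the Elusimicrobia midpoint (−0.11) matches percentage points. The Firmicutes midpoint (−0.055) is near a proportion (−0.066). The Proteobacteria midpoint (0.19) matches neither 2.73 points nor 0.027. No weight is placed on such a rebuild.

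**Conclusion.** The concern holds. No between-group result in Table 4 survives correction: BH q is 0.168 over 14 rows and 0.208 over 13 phyla, and Holm p-values are at least 0.518. The smallest q that rounding allows is 0.166, and the three named phyla cannot fall below 0.128 in a 16-phylum family. The statement that the milk raised the sum, and the relationship claimed for three phyla, are therefore exploratory. The Table 3 sentence misdescribes its table whatever view is taken of multiplicity.

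This rests on the printed p-values, an assumed two-sided 0.05 level, and the natural reading of the ANOVA as milk against no milk. Since the analysed variable is not stated, the p-values may change once it is clarified. Confidence is high for the correction of the printed values.

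**What to change.** 1. State in the SAP and under Table 4 whether the ANOVA used second-test values or changes, and on which scale.
2. Fix one family, preferably all 16 phyla, with a permutation test where an arm is all zero. Print BH q-values from the final p-values, and label all phylum results and the sum exploratory.
3. Replace the summary below Table 4 with: *Within the main group Firmicutes rose and Proteobacteria fell; between-group differences were nominal only and did not remain significant after Benjamini-Hochberg correction.* Give the q-values of the chosen family (as now printed, 0.17 for the 14 rows or 0.21 for the 13 phyla), and revise the sentence if re-analysis changes them.
4. Reword the Table 3 sentence as two within-group results, and refer to the last row of Table 4 (p=0.037, unadjusted) for the between-group test.
5. From the existing sequencing data, where resolution allows, report a between-group comparison of one alpha-diversity index and of short-chain-fatty-acid producers, declared post hoc.

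The cost is re-analysis of existing data and edits to the text and Table 4, with no new patients or samples. The downside is that the phylum findings become exploratory and the added analyses are post hoc.

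### The Bacteroidetes+Firmicutes sum that leads the microbiome conclusion is not pre-specified in the SAP, and its between-arm difference comes entirely from Firmicutes

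*Combined protocol and SAP*

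**What the plan says.** The Gut microbiota part of the Statistical Analysis Plan plans paired before-after tests and a single-factor analysis of variance on gut microbiota indicators. It names no combined indicator, no leading phylum and no rule for multiple testing.

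The sum of Bacteroidetes and Firmicutes first appears in the Results section, above Table 3. The reason given is that these two phyla make up the largest share of the microbiota. The text continues: "Summarizing their values in the main and control groups, we can see that their content increased in the former and decreased in the latter". The next sentence reports a significant difference in these phyla between the main and control groups and cites Table 3, whose figures are "77,63% 81,3% 0,026 78,76% 75,87% 0,213".

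Table 4 then gives one-way ANOVA p-values in 14 rows, among them Bacteroidetes ("Bacteroidetes 0,180"), Firmicutes (0.048) and the sum (0.037). The closing paragraph says that milk intake "primarily contributed to an increase in the content of the sum of two major phyla of gut microbiota", and adds that Firmicutes was the more notable of the two.

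**The concern.** A combined measure that is absent from the plan carries the first microbiome conclusion. If one component produces the whole between-arm difference, the combined measure adds no support beyond that component. A reader of Table 4 who sees 0.048 for Firmicutes and 0.037 for the sum may take them as two findings. A reader of the sentences around Table 3 may conclude that both phyla rose with milk, and that the arms were shown to differ on both. At stake is what the trial says it found in the microbiome, and how strongly.

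**Working it through.** **Inputs** (mean percentages)
- Main arm, Table 1: "Bacteroidetes 32,32% 29,43% -0,01; 0,07 0,178" and "Firmicutes 45,31% 51,87% -0,09; -0,02 0,001".
- Control arm, Table 2: "Bacteroidetes 32,27% 29,77% -0,06; 0,08 0,754" and "Firmicutes 46,5% 46,1% -0,06; 0,07 0,899".

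**Step 1. Rebuild Table 3 (Bacteroidetes + Firmicutes)**
- Main: 32.32 + 45.31 = 77.63; 29.43 + 51.87 = 81.30. Both match.
- Control: 32.27 + 46.5 = 78.77 (stated 78.76, a rounding difference of 0.01); 29.77 + 46.1 = 75.87. Matches.

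**Step 2. Change within each arm (points)**

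| | Firmicutes | Bacteroidetes | Sum |
|---|---|---|---|
| Main | 51.87 - 45.31 = +6.56 | 29.43 - 32.32 = -2.89 | +3.67 |
| Control | 46.1 - 46.5 = -0.40 | 29.77 - 32.27 = -2.50 | -2.90 |

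**Step 3. Difference in change, main minus control**
- Firmicutes: 6.56 - (-0.40) = +6.96
- Bacteroidetes: -2.89 - (-2.50) = -0.39
- Sum: 6.96 - 0.39 = +6.57. From Table 3 directly: (81.3 - 77.63) - (75.87 - 78.76) = +6.56.
- Shares: 6.96 / 6.57 = 106% Firmicutes; -0.39 / 6.57 = -6% Bacteroidetes.

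**Step 4. Other ways of taking the contrast**
- Second test only: Firmicutes 51.87 - 46.1 = +5.77; Bacteroidetes 29.43 - 29.77 = -0.34; sum +5.43; Firmicutes share 106%.
- Changes quoted in the text (main -3.03 and +7.62; control -2.5 and -0.4): Firmicutes +8.02; Bacteroidetes -0.53; sum +7.49; Firmicutes share 107%.

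**Step 5. Between-arm evidence**
- Table 3 holds two Wilcoxon p-values, 0.026 (main) and 0.213 (control). Each is a before-after test within one arm, so neither compares the arms.
- The between-arm p-values are in Table 4: Bacteroidetes 0.180, Firmicutes 0.048, sum 0.037.
- Table 4 has 14 tests and no stated adjustment. Bonferroni threshold: 0.05 / 14 = 0.0036. The smallest p, for the sum, becomes 0.037 × 14 = 0.518. Under Benjamini-Hochberg the smallest adjusted value is 0.048 × 14 / 4 = 0.168, because 0.048 is the fourth smallest p.

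**Step 6. Text against table, main arm**
- The opening paragraph of the microbiota results gives a Bacteroidetes fall of 3.03 and a Firmicutes rise of 7.62, a net +4.59.
- Table 1 gives -2.89 and +6.56; Table 3 gives a net +3.67. These do not agree.

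The ANOVA p-values cannot be recomputed. No standard deviations or patient-level microbiome data are given, and the plan does not say whether the ANOVA used second-test values or changes.

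**The case against.** Three stronger readings are tempting, and the documents support none of them.

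- A reader might infer that the sum was chosen after the data were seen. The documents do not date the choice, and they give a reason based on the size of the two phyla. The SAP names no phylum at all, so Firmicutes alone is no more pre-specified than the sum. What can be said is that the sum is not pre-specified.
- A reader might infer that the report claims a rise in both phyla and hides the fall in Bacteroidetes. The closing sentence claims a rise in the sum, which did occur in the main arm (+3.67 points), and it singles out Firmicutes. The opening paragraph lists Bacteroidetes among the phyla that decreased. The fair criticism is of wording that invites a two-phylum reading.
- A reader might infer that one phylum is formally counted as two findings. The sentence introducing Table 4 names only Firmicutes, Elusimicrobia and Proteobacteria as significant, and the row for the sum is openly labelled. The overlap matters when the two rows are read together and when the sum leads the conclusion.

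Two technical objections also have force. First, the finding that Firmicutes supplies the whole difference holds only for the between-arm contrast of means. Within the control arm, most of the fall in the sum is Bacteroidetes (2.50 of 2.90), and the sum also tells the reader about the combined share of all other phyla.

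Second, the split is of point estimates without standard errors, and the printed confidence intervals do not centre on the mean changes. Control Bacteroidetes centres on 0.01, against a raw fall of 0.025. If the intervals are read as proportions, before minus after, their centres give Firmicutes 5.5 - (-0.5) = +6.0 points and Bacteroidetes -3.0 - (-1.0) = -2.0, so Firmicutes still drives the sum. That scale is doubtful: the main-arm Proteobacteria interval is 0.1 to 0.28, against a raw fall of 9.25 - 6.52 = 2.73 points (0.0273). I therefore attach no precision to the split, and I do not treat 0.180 as a test of the -0.39 points.

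**Conclusion.** The point holds in this form. An unplanned combined measure leads the microbiome conclusion, and its between-arm difference in mean change (+6.57 points, or +6.56 from Table 3) comes entirely from Firmicutes (+6.96), with Bacteroidetes contributing -0.39. The Firmicutes share is 106% to 107% on the three versions of the contrast in steps 3 and 4. The Table 4 rows for Firmicutes and for the sum are overlapping evidence, and neither survives adjustment across the 14 tests.

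The sentence citing Table 3 claims a between-group difference that Table 3 cannot show. For Bacteroidetes, Table 4 reports no significant difference.

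This rests on the means printed in Tables 1 and 2, which reproduce Table 3 to within 0.01. It does not depend on when or why the sum was chosen. It also does not establish that Firmicutes rose relative to control, since that rests on an unadjusted p of 0.048.

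**What to change.** - Label the sum as not pre-specified and exploratory, in Table 4 and in the text, and do not lead the conclusion with it.
- Correct the sentence that cites Table 3 so that it refers to the between-arm test in Table 4 and to the sum, not to both phyla.
- Report the phyla separately. State that the between-arm difference in the sum is driven by Firmicutes, with a nominal, unadjusted p of 0.048 among 14 tests. State that mean Bacteroidetes fell in both arms (Table 1: -2.89; Table 2: -2.50) with no significant between-arm difference (p = 0.180).
- Say whether the ANOVA used second-test values or changes.
- Reconcile the main-arm changes quoted in the text (-3.03 and +7.62) with Table 1 (-2.89 and +6.56) before any of these figures goes into the revised conclusion.

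The cost is rewording and a check of the source figures, with no new data. The microbiome conclusion becomes slightly less favourable.
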